**Elimination criteria:**

- Patients who do not comply with the follow-up time and drug administration.
- Patients who do not comply with proper drug intake.
- Patients with intolerance or severe adverse effects to the components of the drug.
- Patients who are unable to undergo FibroScan® examination due to technical limitations.

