## **HYPOTHESIS**

The administration of the combination of alpha-lipoic acid and Silybum marianum (LUDLEV®) in combination with a Mediterranean diet reduces the degree of fibrosis and steatosis in patients with MAFLD as assessed by kPa and CAP measurements after 24 weeks of treatment.

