### **Exclusion criteria:**

- Patients who meet diagnostic criteria for MAFLD with normal weight.
- Patients with terminal illness, cancer, or end-stage renal disease on renal replacement therapy.
- Pregnant women.
- Patients who are unable to understand or follow the study protocol.
- Sensitivity to the components of the formula.

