**Interventions**

Patients included in the study will be randomly distributed in a 1:1 ratio to receive the two treatment regimens.

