#### **4. Follow-up and surveillance**

1. Physical activity: It will be evaluated by means of the international physical activity questionnaire (IPAQ) that categorizes the levels of physical activity in: low (category 1), moderate (category 2) and high (category 3) according to the intensity, frequency and duration of the training. The recommendation will be made not to modify the usual training plan.
2. Nutritional plan: The monitoring will be carried out in a personalized way through a monthly face-to-face nutritional consultation.
3. Pharmacological treatment: The adherence to the pharmacological treatment will be monitored through a monthly telephone interview. Telephone assistance will be available to resolve doubts and report adverse effects.

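### The elimination criteria act on events after randomisation and do not say what elimination does; read in the usual way, they remove randomised patients and can bias the week-24 comparison

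*Protocol*

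**What the plan says.** The protocol has three separate lists: Inclusion criteria, Exclusion criteria and Elimination criteria. The first three of the four elimination items are:

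- the first, on attendance and dosing: "Patients who do not comply with the follow-up time and drug administration"
- the second, on how the product is taken: "Patients who do not comply with proper drug intake"
- the third, on tolerability: "Patients with intolerance or severe adverse effects to the components of the drug"

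The fourth concerns patients in whom FibroScan is not technically possible. It could apply at baseline and is not part of this point.

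Under Interventions, "Patients included in the study will be randomly distributed in a 1:1 ratio to receive the two treatment regimens". Under Follow-up and surveillance, "The adherence to the pharmacological treatment will be monitored through a monthly telephone interview". The Hypothesis section places the effect on fibrosis and steatosis "as assessed by kPa and CAP measurements after 24 weeks of treatment".

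The protocol does not say what happens to an eliminated patient, and it gives no threshold for complying or for proper intake. Nothing in the sections on interventions, assessments, follow-up or analysis says that such a patient stays in the planned visits or in the comparison.

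**The concern.** A rule that removes patients for what happens to them on treatment selects on a consequence of treatment. Randomisation makes the two arms comparable at allocation. It does not keep them comparable once patients are dropped for intolerance or poor intake.

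Two features make unequal, outcome-related removal plausible here. First, the intolerance item refers to the components of the drug, and only Group B receives the active components. Second, patients who take the product poorly may also follow the diet poorly, and the Background links diet and weight loss to liver fat, inflammation and fibrosis.

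At stake is whether the week-24 kPa and CAP comparison answers the question for the patients randomised or only for those who tolerated and complied. In the second case its nominal 5% error rate is not assured. If eliminated patients also stop attending the week-12 and week-24 scans, no later analysis plan can recover their data.

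**Working it through.** **Are the three items really post-randomisation?** Two comparisons within the protocol show that they are.

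- The Exclusion criteria already cover "Sensitivity to the components of the formula" and "Patients who are unable to understand or follow the study protocol". The elimination items on intolerance and compliance would duplicate these if they were screening items.
- Drug adherence is observed by monthly telephone interview during treatment, and no run-in on study drug is described. Compliance and intolerance can therefore be seen only after allocation.

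**How large could the effect be?** The protocol has no figure of its own to reproduce on this point.

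| Input | Value | Source |
|---|---|---|
| Patients per arm | 50/2 = 25 | Sample size calculation; 1:1 allocation |
| Significance level | 0.05 | Analysis of the results; two-sided is assumed |
| True treatment effect | none | assumed, to isolate the bias |
| Proportion removed, *d* | 4% to 30%, by arm | assumed |
| Correlation of adherence with outcome, *r* | 0, 0.3, 0.5 | assumed |

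*Continuous outcome (such as kPa or CAP change).* A patient is removed if latent adherence falls below its *d*-quantile z_d. The mean of the patients left then shifts by

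r × g(d), with g(d) = φ(z_d)/(1 − d).

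The bias is r × [g(d_active) − g(d_placebo)], in favour of the arm that loses more patients.

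- g(0.04) = 0.0862/0.96 = 0.090
- g(0.16) = 0.2433/0.84 = 0.290
- g(0.20) = 0.2800/0.80 = 0.350
- g(0.24) = 0.3109/0.76 = 0.409
- g(0.30) = 0.3477/0.70 = 0.497

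For example, 24% against 4% gives 0.409 − 0.090 = 0.319, and 0.319 × 0.3 = 0.096 SD or 0.319 × 0.5 = 0.160 SD. Type I error comes from 100,000 simulated trials with a pooled t-test.

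| Removed, active vs placebo | Bias, r = 0.3 / 0.5 | Type I error, r = 0.3 / 0.5 |
|---|---|---|
| 24% vs 4% (about 6 vs 1 patients) | 0.10 / 0.16 SD | 6.1% / 8.2% |
| 16% vs 4% (4 vs 1) | 0.06 / 0.10 SD | 5.3% / 6.4% |
| 30% vs 20% | 0.04 / 0.07 SD | 5.1% / 5.5% |
| 20% vs 20%, or 25% vs 25% | 0 | about 5% |
| any of these splits with r = 0 | 0 | about 5% |

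*Responder outcome (the type used in the sample size calculation).* Let *p* be the true response rate in both arms, *d* = 25% the share of active patients removed, none removed from placebo, and *q* the response rate among those removed. The bias is (p − d·q)/(1 − d) − p. Rejection is by Fisher's exact test, 19 vs 25 patients.

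| p | q = 0 | q = 10% | q = 20% | Fisher with no selection |
|---|---|---|---|---|
| 15% (protocol's comparator rate) | +5.0 points, 4.3% | +1.7 points, 2.6% | −1.7 points, 2.1% | 2.2% |
| 40% (assumed) | +13.3 points, 10.0% | +10.0 points, 6.9% | +6.7 points, 4.8% | 3.0% |

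For instance, with p = 15% and q = 0: 0.15/0.75 − 0.15 = 0.05. Fisher's test is conservative at these sizes, so the last column is the fairer baseline. The rate passes 5% only at p of about 18%, 27% or 42% for q = 0, 10% or 20%.

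**The case against.** The strongest objection is that the protocol never says eliminated patients leave the analysis. If elimination means only that study product stops, this bias does not arise, and what the text proves is an undefined term. That is fair, and it is why the bias is stated conditionally. But the list sits beside the inclusion and exclusion criteria, and its natural reading is removal from the study. Nothing elsewhere in the protocol rules that reading out.

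A second objection is that analysis sets commonly belong in an SAP, which is not at hand. That also stands in part: the absence of a named intention-to-treat set is not the complaint. The complaint is that the protocol states a removal rule that governs conduct. An SAP can define a population, but it cannot supply scans that were never done.

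Third, part of the first item is ordinary loss to follow-up, for which the sample size allows 10 of 50 patients. The allowance protects numbers, not comparability. How patients without a week-24 scan are analysed can be left to the SAP.

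Last, every rate in the illustration is assumed and most results are small. Double-blinding makes a strong imbalance on the two compliance items less likely. The responder figures are less relevant, since the hypothesis concerns kPa and CAP. All of this limits the size of the concern but does not remove it.

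**Conclusion.** The concern holds and should be fixed. Three elimination criteria depend on events after randomised treatment starts, and the protocol leaves their consequence open. On the ordinary reading, following them yields a selected week-24 comparison.

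Its bias cannot be sized or signed from the documents. Under the assumptions above, the continuous-outcome bias runs from 0 to 0.16 SD and the type I error from about 5% to 8%. The upper end needs both a marked imbalance (24% vs 4% removed) and r = 0.5. In the responder case at the protocol's 15% comparator rate, the false-positive rate stays below 5% throughout. There is no bias if removal is equal in both arms by the same mechanism or unrelated to outcome. Confidence is medium, because the meaning of elimination is inferred.

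**What to change.** Define elimination in the protocol. State that meeting any of the first three criteria, whatever happens to study treatment, does not remove a patient from the planned week-12 and week-24 assessments or from the primary analysis. Analyse all randomised patients in their allocated arm, and report a complier-only analysis as a sensitivity analysis.

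Two small clarifications can go in with it: at which scan the FibroScan criterion applies, and that adverse effects in patients who meet these criteria are still counted.

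The cost is a change of wording plus some effort to bring off-treatment patients back for visits already in the schedule. The estimated effect may be smaller than among compliers alone. The change sets no rule on stopping or dosing.

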### **Specific Objectives:**

- To assess the effects of administering alpha-lipoic acid and Silybum marianum (LUDLEV® 300 mg/46.2 mg) in combination with a Mediterranean diet versus placebo plus a Mediterranean diet on fibrosis and steatosis in patients with MAFLD after 12 weeks of treatment.
- To evaluate changes in fibrosis measured by kPa using FibroScan® elastography after 12 and 24 weeks of administering alpha-lipoic acid and Silybum marianum (LUDLEV® 300 mg/46.2 mg) every 12 hours in combination with a Mediterranean diet, compared to placebo plus a Mediterranean diet in patients with MAFLD.
- To assess changes in the controlled attenuation parameter (CAP) measured by FibroScan® elastography after 12 and 24 weeks of administering alpha-lipoic acid and silybum marianum (LUDLEV® 300 mg/46.2 mg) every 12 hours in combination with a Mediterranean diet, compared to placebo plus a Mediterranean diet in patients with MAFLD.
- To evaluate biochemical improvement after 12 and 24 weeks of administering alpha-lipoic acid and Silybum marianum (LUDLEV® 300 mg/46.2 mg) every 12 hours in combination with a Mediterranean diet, compared to placebo plus a Mediterranean diet in patients with MAFLD.
- To assess weight loss and changes in body composition after 12 and 24 weeks of administering alpha-lipoic acid and Silybum marianum (LUDLEV® 300 mg/46.2 mg) every 12 hours in combination with a Mediterranean diet, compared to a Mediterranean diet alone in patients with MAFLD.

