## 1. Initial assessment and follow-up

Initial medical assessment including:

1. Complete medical history
2. Hepatic ultrasound showing evidence of hepatic steatosis. The degree of hepatic steatosis will be determined according to Hamaguchi score ( $\geq 3$  points) classifying it as follows: absent (0 points), mild (1 point), moderate (2 points) and severe (3 points). This scoring system has a maximum sum of 6 points and considers hepatorenal echo contrast, hepatic brightness, deep attenuation and vascular visualization with a specificity of 100% and sensitivity of 91.7%.
3. The risk of fibrosis will be determined according to FIB-4, NAFLD score or APRI. FIB-4 is considered high risk of fibrosis score  $\geq 3.25$ , indeterminate 1.45-3.25 and absent  $\leq 1.45$ ; in NAFLD score high risk with  $\geq 0.675$ , indeterminate -1.455 to 0.675 and absent  $\leq -1.455$ ; in APRI high risk of significant fibrosis with score  $\geq 1.5$ , indeterminate 0.5-1.5 and absent  $\leq 0.5$ .
4. Transitional liver elastography with FibroScan® will be performed at baseline, 12 and 24 weeks follow-up to estimate hepatic fatty infiltration according to the controlled attenuation parameter (CAP) and hepatic stiffness in kilopascals (kpa). Considering fibrosis stages the following cut-off points F0  $\leq 6.4$ kpa, F1 6.5 to 6.9 kpa, F2 7 to 8.6kpa, F3 8.7 to 10kpa, F3-F4 10.1 to 15 kpa and F4  $\geq 15$ kpa. For hepatic fatty infiltration is considered by CAP S0  $\leq 247$ , S1 between 248 to 267, S2 268 to 279 and S3  $\geq 280$ . 10 representative valid measurements with success rate (IQR) 30% are considered. All measurements will be taken by the same operator.
5. At baseline, 12 and 24 weeks follow-up the following laboratory studies will be performed: blood biometry, blood chemistry, liver function tests, lipid profile and C-reactive protein, serum insulin, HOMA calculation.
6. The study of viral hepatitis type B and C will be performed at the beginning of the study.

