## **SCHEDULE OF ACTIVITIES 2022-2023**

ACTIVITIES	APRIL MAY	JUNE JULY	AGO SEP	OCT NOV	DIC ENE	FEB MARCH	APRIL MAY	JUN JUL	AGO SEP
Elaboration and approval of the research project	X								
Elaboration of placebo		X							
Patient recruitment - Medical and nutritional evaluation. - Initial laboratory studies - Nutritional counseling to establish a Mediterranean style dietary plan. - Initial FibroScan® study			X	X	X				
Medical and nutritional follow-up and monitoring (12 weeks) - Monitoring of compliance with the nutritional plan and treatment. - Laboratory studies - FibroScan® study					X	X	X		

Medical and nutritional follow-up and monitoring (24 weeks) - Monitoring of compliance with the nutritional plan and treatment. - Laboratory studies - FibroScan® study						X	X	X	
Data processing								X	
Statistical analysis of results								X	
Reporting the results Manuscript writing								X	
Dissemination									X

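### Technical inability to have a FibroScan is an elimination criterion with no time limit rather than a pre-randomisation exclusion, so a randomised patient can be removed, and usable non-scan data lost, avoidably.

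*Protocol*

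**What the plan says.** The protocol's Elimination criteria have four items. Two concern compliance, for example "Patients who do not comply with the follow-up time and drug administration", and one concerns intolerance or severe adverse effects. The fourth is of a different kind: "Patients who are unable to undergo FibroScan® examination due to technical limitations". It concerns whether a measurement can be made, and it names no visit.

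The Exclusion criteria have five items, from "Patients who meet diagnostic criteria for MAFLD with normal weight" to "Sensitivity to the components of the formula". None mentions FibroScan, and neither do the Inclusion criteria.

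On timing, item 4 of section 1 (Initial assessment and follow-up) says that elastography "will be performed at baseline, 12 and 24 weeks follow-up to estimate hepatic fatty infiltration", and also to measure stiffness. The Schedule of Activities lists "Initial FibroScan® study" in the patient recruitment row. Allocation is described afterwards, in section 3 (Randomization by groups).

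On outcomes, the Hypothesis concerns fibrosis and steatosis "as assessed by kPa and CAP measurements after 24 weeks of treatment". The Specific Objectives add outcomes that do not use the device: "To evaluate biochemical improvement after 12 and 24 weeks", and weight and body composition at the same two times.

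**The concern.** Whether a patient can be scanned can be found out at the baseline scan, before allocation. A rule that depends on it belongs among the entry criteria, where it costs a screen failure and leaves the randomised comparison untouched. Placed among the elimination rules, it acts on patients already in the trial.

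Two things are at stake. First, a place in a 50-patient trial can go to someone who cannot contribute a change in CAP or kPa. Second, a later scan failure, which is a problem with one instrument at one visit, becomes a reason to remove the whole patient. Valid laboratory and anthropometric data may go with it, and the groups compared are then no longer the groups randomised.

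**Working it through.** The point is about where a rule is placed, so the main check is to follow the rule through the protocol.

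**Does the elimination list act after entry?** The other three items (adherence to follow-up and drug administration, proper intake, intolerance or severe adverse effects) can arise only once treatment has begun. The fourth item sits among them and has no timing of its own.

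**Does any entry rule catch an unscannable patient?** No inclusion or exclusion item names the scan. Steatosis at the initial assessment is shown by hepatic ultrasound (section 1, item 2), so a patient can qualify without a usable FibroScan.

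**Case A: the baseline scan fails.** No entry criterion is clearly breached, so the patient can be randomised. The elimination item then applies.

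**Case B: the baseline scan is valid and the week-12 or week-24 scan fails.** The elimination item applies at that visit. The outcomes compare as follows:

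| Outcome | Needs FibroScan? | Where specified |
|---|---|---|
| CAP, kPa | Yes | Section 1, item 4 |
| Laboratory tests, HOMA | No | Section 1, item 5 |
| Anthropometry, impedance | No | Section 2, item 4 |

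Only the first row is missing because of the failure. Eliminating the patient puts the other two rows at risk as well.

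**Size.** The protocol gives no failure rate, so a range has to be assumed. The Sample size calculation adds 25% of 40 (40 × 0.25 = 10) to reach 40 + 10 = 50.

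- Assumed 3% affected: 0.03 × 50 = 1.5 patients.
- Assumed 10% affected: 0.10 × 50 = 5 patients, or 5/10 = half of the loss allowance.

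This range does not separate Case A from Case B. A failure found and acted on before allocation would use none of the allowance.

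**Is power the issue?** Take the planning rates of 70% and 15%, a two-sided 0.05 test, the full 25% loss, and scan failures on top:

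| Assumed scan failure | Patients left | Per arm | Power, normal approximation | Power, Fisher exact |
|---|---|---|---|---|
| 3% | 50 × (1 − 0.25 − 0.03) = 36 | 18 | 95% | 91% |
| 15% (deliberately high) | 50 × (1 − 0.25 − 0.15) = 30 | 15 | 90% | 80% |

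So power for the planning difference is not the problem. That difference concerns ultrasound-graded steatosis, so the table says nothing about power for CAP or kPa. The stated 40 is taken as given here; whether it follows from its inputs is a separate matter.

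**The case against.** The strongest reply is that this is largely a labelling problem. The baseline scan precedes randomisation in the order of the protocol. An item with no time limit can also be applied at that scan, and a sensible investigator would not randomise a patient known to be unscannable. One exclusion criterion also covers patients who cannot understand or follow the protocol, and three scans are part of that protocol. This stands in part: good practice at the site could make Case A rare. But the exclusion item is about the patient's capacity and does not clearly reach a technical failure. The protocol should not depend on staff applying an elimination rule as if it were an entry rule.

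A second reply is that the protocol nowhere says that elimination deletes a patient from every outcome. It could mean leaving only the scan analyses, and an SAP, not available here, might define the analysis sets. This also stands in part: total loss is the plain reading of an undefined word, not a stated rule. However, an SAP cannot screen out a patient before allocation or recover visits that were never made.

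A reader might go further. Because normal-weight patients are excluded, one might infer that scan failure tracks body size, so that patients who lose least weight fail later scans and the rule removes poor responders. The documents do not support this. They give no link between scan failure and body size or response. The inference is also doubtful on its own terms: a patient with a valid baseline scan who loses little weight keeps roughly the body size that was scannable.

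Finally, the compliance and intolerance items raise post-randomisation selection more directly than this one. That is fair, but it does not make this item correct.

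**Conclusion.** The concern holds in a limited form. The protocol makes scan infeasibility a ground for eliminating patients, sets no time limit, and does not use the baseline scan as an entry condition. Followed as written, it permits randomising and then removing an unscannable patient. It also permits removing a patient for a later scan failure that affects CAP and kPa alone.

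The number affected cannot be known from the document; 1.5 to 5 of 50 is an illustration under an assumed 3% to 10% covering baseline and later failures together. The conclusion does not depend on that range. Nor does it depend on lost power or on failures being related to response, neither of which is shown. It rests on the rule's position, its lack of timing, and the presence of outcomes that need no scan. It is a modest point, worth correcting because the correction is nearly free.

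**What to change.** Make three changes to the protocol:

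1. Add to the Exclusion criteria: unable to obtain a valid FibroScan at baseline. State that the baseline scan is completed before randomisation, and tie validity to the measurement condition already in section 1, item 4.
2. Delete the fourth item from the Elimination criteria.
3. State that a failed scan at week 12 or week 24 makes only that visit's CAP and kPa missing, and that the patient stays in follow-up and in all other outcomes.

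These are changes of wording. The baseline scan is already scheduled, so no procedure is added, and nothing about treatment changes. The small downside is a few screen failures before randomisation.

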**Sample size calculation**

It is calculated based on the previous study by Martinez Rodriguez et al.( Clinical and Experimental Pharmacology Clin Exp Pharmacol 2014, 5:1) where forty patients with NAFLD were randomized into two groups to receive metformin 1500 mg q.a.d. or metformin 1500 mg q.a.d. + (15 mcg)-methionine (3 mg)-alpha lipoic acid (200 mg) group for 24 weeks, and showed a 70% versus 15% decrease in ultrasound-graded steatosis ( $p < 0.001$ ) in patients receiving alpha lipoic acid. Taking into account this difference in proportions, considering a power of 80%, alpha error of 20% and confidence interval of 95%, 20 pairs (40 patients) are required to be randomized. If we consider a loss of 25% ( $n=10$ ), a total sample of 50 patients would be required.

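### The 80% power stated for 20 per arm does not follow from the protocol's own ultrasound inputs (about 93–96%), and no CAP or kPa figure, the outcomes of the hypothesis, enters the calculation

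*Protocol*

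**What the plan says.** Protocol, Sample size calculation: the basis is an earlier 40-patient, 24-week metformin-based trial that "showed a 70% versus 15% decrease in ultrasound-graded steatosis". The error rates are given as "considering a power of 80%, alpha error of 20% and confidence interval of 95"%. The result is that "20 pairs (40 patients) are required to be randomized". The allowance for attrition follows: "If we consider a loss of 25"%, taken as 10 patients, so that "a total sample of 50 patients would be required".

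Protocol, Hypothesis: the effect on fibrosis and steatosis is judged "as assessed by kPa and CAP measurements after 24 weeks of treatment".

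Protocol, Specific Objectives: "To evaluate changes in fibrosis measured by kPa using" FibroScan, and "To assess changes in the controlled attenuation parameter (CAP) measured by" the same device, each at 12 and 24 weeks.

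Protocol, Initial assessment and follow-up: item 4 times FibroScan at baseline, 12 and 24 weeks. Item 2 describes the ultrasound grading within the initial assessment and gives it no follow-up time. Protocol, Analysis of the results, sets significance at p below 0.05.

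**The concern.** There are two separate faults.

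- **Outcome.** The number is derived from a proportion improving on ultrasound grade. That outcome has no scheduled follow-up measurement in this trial and is not the one named in the hypothesis. Fibrosis does not enter the calculation at all.
- **Arithmetic.** A difference of 55 percentage points is very large, and 20 per arm is more than 80% power requires. The printed alpha of 20% is incompatible with the rest of its own sentence, so a reader cannot tell which error rate was used.

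What is at stake is how a null result is read. A non-significant CAP or kPa comparison could be reported as coming from a trial with 80% power, although the protocol contains nothing that supports that figure for either outcome.

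**Working it through.** **Inputs.** From Sample size calculation: p1 = 0.70, p2 = 0.15, power 80%, alpha printed as 20% beside a 95% interval, 20 per arm, 50 in total after a loss of 10. From Interventions: 1:1 allocation. From Analysis of the results: threshold 0.05. Sidedness is not stated; I take two-sided.

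**1. Attempt to reproduce 20 per arm.** Pooled-variance formula:

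n = [z(1−α/2)·√(2p̄(1−p̄)) + z(0.80)·√(p1(1−p1) + p2(1−p2))]² / (p1−p2)², with p̄ = 0.425 and p1−p2 = 0.55.

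- α = 0.05: (1.370 + 0.489)² / 0.3025 = 11.4, so 12 per arm; with continuity correction 14.8, so 15.
- Exact Fisher test at 0.05: power is 0.796 at 15 per arm and 0.844 at 16, so 16.
- α = 0.20 taken literally: (0.896 + 0.489)² / 0.3025 = 6.3, so 7; with continuity correction 9.6, so 10.
- Other readings at 80% power: one-sided 0.05 gives 9 (13 corrected), the arcsine formula 12, the unpooled formula 9, and McNemar's test for literal pairs (independence within pairs assumed) 14 pairs.

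No reading returns 20.

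**2. Power that 20 per arm actually have for 70% vs 15%, two-sided 0.05.**

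- Exact enumeration: chi-square 0.963, Fisher 0.931.
- Normal approximation: Φ[(0.55 − 1.96 × 0.1563) / 0.1299] = Φ(1.875) = 0.970.
- Against a 15% control response, 80% power is already reached at an active response of about 55% (chi-square) or 60% (Fisher).

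**3. What 20 per arm offer for a continuous outcome.** The protocol gives no SD for CAP or kPa, so the result is in SD units. For an unadjusted two-sample t-test, two-sided 0.05, noncentral t, the standardised difference detectable with 80% power is:

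| Evaluable | Arms | Detectable difference |
|---|---|---|
| 40 (50 less the stated 10) | 20/20 | 0.909 SD |
| about 37 (a full 25% of 50, i.e. 12.5, lost) | 18/19 | 0.948 SD |
| 50 (no loss) | 25/25 | 0.809 SD |

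At 20/20, power for 0.5 SD is 0.338. A rank test on normal data needs about 0.909/√0.955 = 0.93 SD.

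**4. Scale, on an assumption only.** If the SD of CAP were 40 to 60 units (not in the protocol), 0.909 SD would be 36 to 55 units. The conclusion does not depend on this.

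**The case against.** The strongest reply has four parts.

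- *For its own inputs the trial is larger than needed, so the error is conservative.* True for ultrasound response. It gives no assurance for CAP or kPa, and the printed derivation still cannot be reproduced.
- *The alpha of 20% is a slip for beta.* Very probably, since it stands beside 80% power. The sentence still needs correcting, and reading alpha as 0.05 does not give 20 per arm either.
- *CAP measures steatosis and the protocol grades it S0 to S3, so sizing on ultrasound steatosis is indirect rather than baseless; and the section never claims 80% power for CAP or kPa.* This stands in part, and is why I call CAP an unstated proxy and reserve the absence of any basis for kPa. The protocol defines no CAP responder and does not link the two scales. Its only power statement is the ultrasound one, so readers will apply it to the stated outcomes.
- *0.91 SD assumes an unadjusted t-test, which the protocol does not specify.* This stands as a caveat. If the analysis adjusted for baseline with an assumed correlation of 0.5 to 0.7, the figure would fall to 0.909 × √(1−0.25) = 0.79 SD or 0.909 × √(1−0.49) = 0.65 SD. The value should be labelled an approximation. It is equally fair that a sensitivity statement discloses the missing target difference without supplying one.

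**Conclusion.** The concern holds; it should be fixed. The more serious part is the outcome mismatch: the stated power has no basis for kPa and only an unstated proxy for CAP. The arithmetic is also wrong as printed. At two-sided 0.05, 20 per arm have 93% (Fisher) to 96% (chi-square) power for 70% vs 15%, not 80%, and 80% would need 12 to 16 per arm. The alpha statement contradicts its own sentence and the analysis section.

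The proportion results assume a two-sided test of two independent groups. The 0.91 SD figure assumes an unadjusted t-test on 40 evaluable patients and moves with attrition and with baseline adjustment. Neither assumption affects the finding that no CAP or kPa input was used.

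**What to change.** Keep enrolment at 50 and rewrite Sample size calculation as follows.

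1. State that the 70% vs 15% calculation concerns ultrasound grade in an earlier trial, and that no CAP or kPa target difference or SD was used to set the number.
2. Correct the alpha of 20% to 0.05, two-sided. The sidedness is an addition, because the protocol does not state it.
3. Replace the 80% claim with text such as: *With 40 evaluable patients (50 less the stated loss of 10), an unadjusted two-sided 5% t-test, used as an approximation, has 80% power for a between-arm difference of about 0.91 SD in a continuous FibroScan outcome (CAP or kPa) at week 24; 0.95 SD if a full 25% of 50 are lost, leaving about 37; 0.81 SD with no loss.* If a rank test is planned, give about 0.93 SD.
4. Label any conversion to CAP units or kPa as resting on an assumed SD.

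The cost is wording only: no extra patients, visits or measurements. The stated sensitivity will look less favourable than the present claim, and 50 will be presented as a fixed number with its sensitivity rather than as derived from a CAP or kPa target.

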#### **5. Analysis of the results**

The analysis of the results, elaboration of figures and tables will be carried out with the statistical program IBS SPSS version 22.0. Nominal and ordinal variables will be described with frequencies and percentages; continuous and discrete variables with measures of central tendency and dispersion according to their distribution. The normality of data distribution will be evaluated with the Kolmogorov-Smirnov test, and nonparametric statistics will be used to evaluate intergroup differences between nominal variables. Non-parametric statistics will be used for ordinal variables. A p-value of less than 0.05 will be considered statistically significant.

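### The sample size paragraph states an alpha of 20% that contradicts the 5% level used elsewhere, and the 20 per arm it calls required does not follow from 70% versus 15% in two unmatched groups

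*Protocol*

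**What the plan says.** The Protocol, under Sample size calculation, takes its effect from an earlier 24-week study of 40 patients randomised into two groups, which "showed a 70% versus 15% decrease in ultrasound-graded steatosis". From that difference it continues: "considering a power of 80%, alpha error of 20% and confidence interval of 95%, 20 pairs (40 patients) are required to be randomized". It then adds 10 patients for a 25% loss and concludes that "a total sample of 50 patients would be required".

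Three other places bear on this calculation:

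- Interventions: patients are "randomly distributed in a 1:1 ratio to receive the two treatment regimens". Section 3, Randomization by groups, describes two groups, A and B. Neither mentions matching or crossover.
- Section 5, Analysis of the results: "A p-value of less than 0.05 will be considered statistically significant".
- Hypothesis and Specific Objectives: fibrosis and steatosis are assessed by FibroScan stiffness (kPa) and CAP, not by ultrasound grade.

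**The concern.** Two stated figures look wrong.

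1. **The alpha.** A 95% confidence interval corresponds to a 5% error level, and the analysis section also uses 0.05. An alpha of 20% is four times that. Since 1 − 0.80 = 0.20, the figure looks like beta under the wrong name.
2. **The required number.** A difference of 55 percentage points is very large, and 20 per arm is more than a two-group comparison at 80% power should need. The word pairs also does not suit a trial that randomises individual patients to two separate groups.

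This paragraph is the only sample size justification in the document. As written, a reader cannot reproduce it, and could not tell from it alone what error rate or what kind of design it assumes.

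**Working it through.** **Inputs.** From Sample size calculation: p1 = 0.70, p2 = 0.15, power 80% (z = 0.8416), and alpha written as 20% next to a 95% interval. From Interventions: 1:1 allocation. From section 5: threshold 0.05. The paragraph states neither sidedness nor test. Two-sided 5% (z = 1.96) is therefore an assumption, and alternatives are shown.

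Difference d = 0.55, so d² = 0.3025. Mean proportion = 0.425. Then 2 × 0.425 × 0.575 = 0.48875, and 0.70 × 0.30 + 0.15 × 0.85 = 0.3375.

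**Step 1. Can the plan's 20 be reproduced for two independent groups?**

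- Pooled formula: n = [1.96 × √0.48875 + 0.8416 × √0.3375]² / 0.3025 = 11.43, so 12 per arm.
- Continuity-corrected: n′ = (n/4) × [1 + √(1 + 4/(n·d))]² with n = 11.43 gives 14.84, so 15 per arm.
- Fisher exact, by enumerating all outcomes: power 0.796 at 15 per arm and 0.844 at 16, so 16 per arm.
- Unpooled formula: (1.96 + 0.8416)² × 0.3375 / 0.3025 = 8.76, so 9 per arm, which is further still from 20.

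**Step 2. Do other readings of the unstated inputs help?** Required number per arm at 80% power:

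| Level | Pooled | Continuity-corrected | Fisher |
|---|---|---|---|
| Two-sided 5% | 12 | 15 | 16 |
| One-sided 5% | 9 | 13 | 12 |
| Two-sided 20% (alpha as written) | 7 | 10 | 9 |
| Stated | 20 | 20 | 20 |

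A one-sided test, or the alpha as written, moves the answer further from 20.

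**Step 3. Where could 20 pairs come from?** The matched-pair (McNemar) formula is [z_α × √s + z_β × √(s − d²)]² / d², where s is the sum of the two discordant-pair proportions. If 0.70 and 0.15 are entered as those proportions, s = 0.85 and s − d² = 0.5475:

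- alpha 5% two-sided: [1.96 × √0.85 + 0.8416 × √0.5475]² / 0.3025 = 19.52, so 20 pairs;
- alpha 20% two-sided: 10.76, so 11 pairs.

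If 70% and 15% are instead treated as marginal rates with independent responses within a pair, the discordant proportions are 0.70 × 0.85 = 0.595 and 0.15 × 0.30 = 0.045. The formula then gives 13.99, so 14 pairs.

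So 20 appears when alpha is 5% and two group response rates are used as discordant-pair proportions.

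**Step 4. What does 20 per arm give?** At two-sided 5%, power for 70% versus 15% is 0.931 by Fisher's test and 0.963 by the chi-square test (exact enumeration).

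**Step 5. The loss allowance.** 25% of 40 is 10, and 40 + 10 = 50. This agrees with the text.

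**The case against.** The strongest reply is that this is a slip of one label with no consequence. The same sentence gives 80% power and a 95% interval, so an informed reader can see that 20% is beta, and the analysis section fixes the working threshold at 0.05. The matched-pair formula also returns both the figure 20 and the word pairs, so the number does have a plausible source. And 12 to 16 rests on an assumed test and sidedness.

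Much of this stands. The threshold for analysis is not in doubt, and the exact per-arm number does depend on the method. But no two-group method tried gives 20 at the stated power, at either the 5% level or the written 20%. The matched-pair origin is an inference, since the protocol names no formula. If it is right, the formula does not fit two unmatched groups and needs an alpha other than the one printed.

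A reader might be tempted to go further in four directions that the document does not support:

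- **That the trial will be analysed at a 20% false-positive rate.** Section 5 sets 0.05.
- **That the trial is too small for its planning contrast.** The stated number exceeds what that contrast needs.
- **That the spare power protects the trial as a whole.** The calculation concerns ultrasound-graded steatosis. It says nothing about power for kPa or CAP.
- **That the loss allowance is miscalculated.** Ten is 20% of 50, but the text reads naturally as 25% of the 40 needed, and on that base the sum is right.

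**Conclusion.** The point holds as a correction of reported design figures. The alpha of 20% is wrong as written, and that conclusion needs no assumption about test or sidedness. The required 20 per arm does not follow from the stated inputs in two independent groups. Assuming a two-sided 5% level and 80% power, the three usual methods give 12, 15 or 16 per arm, that is 24 to 32 patients in total rather than 40.

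The discrepancy is conservative, but only for a 70% versus 15% difference in ultrasound-graded steatosis, where 20 per arm give about 93% power (two-sided Fisher exact). That beta was meant is very likely. That a matched-pair formula was used is possible and no more than that. That the paragraph names no test is not in itself the fault; the fault lies in the figures it does state.

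**What to change.** Revise the one paragraph under Sample size calculation:

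- State a two-sided alpha of 5% and a beta of 20% (power 80%).
- Replace pairs with 20 patients per arm, and name the test for two independent groups that was used.
- Present 20 per arm as the planned number, not the minimum: it gives more than 80% power (about 93% by two-sided Fisher exact) for a 70% versus 15% difference in ultrasound-graded steatosis. If another test is named, quote the power for that test.
- Add that this power does not carry over to the kPa and CAP outcomes of the Hypothesis and Specific Objectives.
- Keep 50 enrolled and the allowance of 10 added to 40. At most, say that the 25% refers to the 40.

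The cost is wording and figures in one paragraph. Patient numbers, visits and the analysis threshold do not change.
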